1 SYNOPSIS

NAME OF THE SPONSOR: Essity Hygiene and Health AB
CLINICAL INVESTIGATION TITLE: An open, single-arm, post-market clinical investigation to verify the ability of TENA SmartCare Change Indicator™ to reduce the number of manual checks between changes of absorbing incontinence products in a home environment.
CLINICAL INVESTIGATION CODE: POWER
INVESTIGATIONAL DEVICE: TENA SmartCare Change Indicator™
OBJECTIVES: Primary Objective To demonstrate performance through the ability to reduce the number of manual checks in-between changes of absorbing incontinence products using the TENA SmartCare Change Indicator compared to Standard of Care. Secondary Objectives 
 - Evaluate safety through analyzing device-related adverse events reported during the investigation. - Evaluate leakage into clothes and/or bed linen. - Evaluate change in skin redness and irritation. - Evaluate usability - Evaluate the number of fecal incidences
OVERALL CLINICAL INVESTIGATION DESIGN: The purpose of this post market clinical investigation is to demonstrate the performance and safety of the TENA SmartCare Change Indicator. The TENA SmartCare Change Indicator is intended for use on individuals, dependent end user (DEU), suffering from Urinary Incontinence (UI) who are cared for in a home environment, by one or more caregivers (CGR). The TENA SmartCare Change Indicator is an accessory to TENA absorbing incontinence products. This clinical investigation is intended to demonstrate that use of TENA SmartCare Change Indicator has the ability to reduce the number of manual checks between daily changes of absorbing incontinence products. Secondarily, the investigation will evaluate number of leakages, skin redness, usability and fecal incidence. Furthermore, the safety will continuously be monitored through analyzing device-related adverse events reported during the investigation.
Statistical calculations support the recruitment of 35 DEUs to account for an estimated premature withdrawal rate of 30%. To demonstrate the primary objective 24 evaluable subjects are needed to complete the investigation.
Prior to initiation of any investigational procedures, applicable informed consents are to be obtained. Each DEU and CGR will meet with the investigator to give informed consent, see section 18.
The clinical investigation is designed to be conducted in the DEU's home environment, for a duration of three (3) weeks + potential incontinence product training and visit window scheduling. The first week will establish an individual baseline for each DEU, during which the number of manual checks between changes of the TENA incontinence product are to be registered continuously in a diary by the CGR. During the second week the CGR will be provided with and

trained in the use of the TENA SmartCare Change Indicator. During the third week the TENA SmartCare Change Indicator is to be used as intended by the manufacturer, while the number of manual checks between changes of the TENA incontinence product are to be registered in a diary by the CGR. The resulting numbers are to be analyzed with regard to the individual baseline in order to evaluate the expected reduction of number of manual checks. In total, the clinical investigation involves eight visits out of which two are optional and conducted as deemed necessary.

Summation of planned contacts/visits:**Visit 0: Initial visit**

This visit will be the screening visit for subjects who have not previously used TENA incontinence products. Only these subjects are to attend this visit, for other subjects this visit corresponds to visit 1. During 7 days after the visit the subject and caregiver will develop familiarity with TENA incontinence products to ensure representative data collection during baseline week and the remainder of the investigation.

At visit 0, the following assessments/procedures will be performed:

- Performed by investigator and designated nurse. CGR, informed consent witness, and DEU visit site, or investigator and nurse visit DEU's home.
- Informed consent DEU and witness as applicable, legally designated representative in case DEU is considered unable to provide informed consent.
- Informed consent CGR.
- Eligibility verification (DEU and CGR).
- Demography (DEU and CGR).
- Medical and surgical history (DEU).
- Relevant concomitant medication (DEU).
- Evaluation of general cognitive function (DEU).
- Physical examination (DEU).
- Skin redness/irritation assessment (DEU).
- Pregnancy test (DEU with childbearing potential).
- Instruction and handover of single-use TENA incontinence products.
- Scheduling of visit 1.

Visit 1: Investigation initiation

This will be the screening visit for subjects and CGRs who did not need to attend Visit 0.

At visit 1, the following assessments/procedures will be performed for those who did not need to attend Visit 0:

- Day 0
- Performed by investigator and designated nurse. CGR, informed consent witness, and DEU visit site, or investigator and nurse visit DEU's home.
- Informed consent DEU and witness as applicable.
- Informed consent CGR.
- Eligibility verification (DEU and CGR).
- Demography (DEU and CGR).
- Medical and surgical history (DEU).
- Relevant concomitant medication (DEU).
- Evaluation of general cognitive function (DEU).
- Physical examination (DEU).
- Skin redness/irritation assessment (DEU).
- Pregnancy test (DEU with childbearing potential).

- Instruction and handover of baseline week diary.
- Instruction and handover of single-use TENA incontinence products.
- Scheduling of visit 2.

At visit 1, the following assessments/procedures will be performed for those who completed visit 0:

- Day 0 (+1-3 days)
- Instruction and handover of baseline week diary.
- Handover of single-use TENA incontinence products.
- Relevant concomitant medication review (DEU).
- Skin redness/irritation assessment (DEU).
- Scheduling of visit 2.

Baseline registrations are to be initiated on the first day following the enrollment, i.e. day 1. If required, additional support will be provided as needed during the course of the clinical investigation.

Visit 2: Initiate baseline week.

- Day 1 (+1-3 days)
- Performed by designated nurse in DEU's home, over phone or video call.
- Confirmation of correct baseline week diary initiation.
- Concomitant medication review (DEU).
- Scheduling of visit 3.

Visit 3: Initiate learning week.

- Day 8 (+1-3 days).
- Performed by designated nurse in DEU's home.
- Confirmation of correct baseline week diary registration.
- Concomitant medication review (DEU).
- Skin redness/irritation assessment (DEU).
- Documentation of AE/ADE (DEU and CGR).
- Handover of TENA SmartCare Change Indicator (including instruction/training/verification of understanding).
- Instruction and handover of learning week diary.
- Handover of single use TENA incontinence products.
- Scheduling of Visit 4/5, as applicable.

Visit 4: Assure correct learning and use as intended (optional visit)

- 1-3 days post visit 3.
- Performed by designated nurse, as required based on need for additional support, e.g. visit/phone call/video call.

In case the visit is conducted the following will be investigated:

- Confirmation of correct learning week diary registration.
- Concomitant medication review (DEU).
- Correct use of TENA SmartCare Change Indicator.
- Documentation of AE/ADE (DEU and CGR) and DD if applicable.
- Scheduling of Visit 5.

Visit 5: Initiate investigation week.

- Visit to be take place at ≥ 7 completed days post Visit 3, but ≤ 10 completed days after Visit 3
- Performed by designated nurse in the DEU's home.
- Confirmation of correct learning week diary.
- Concomitant medication review (DEU).
- Skin redness/irritation assessment (DEU).
- Documentation/follow-up of AEs/ADEs (DEU and CGR) and DDs as applicable.
- Instruction and handover of investigational week diary.
- Handover of single use TENA incontinence products.
- Scheduling of visit 6/7, as applicable.
- Questionnaire completion (CGR);
 - o Usability

Visit 6: Additional support, if needed (optional visit).

- 1-2 days post visit 5.
- Performed by designated nurse, as required based on need for additional support, e.g. visit/phone call/video call

In case the visit is conducted the following will be investigated:

- Confirmation of correct investigational week diary registration.
- Concomitant medication review (DEU).
- Correct use of TENA SmartCare Change Indicator.
- Documentation of AEs/ADEs (DEU and CGR) and DDs, or follow-up as applicable.
- Scheduling of visit 7, as applicable.

Visit 7: Investigation completion and termination.

- ≥ 7 completed days post Visit 5.
- Performed by investigator and designated nurse in the DEU's home or at site.
- Confirmation of correct investigational week diary registration.
- Concomitant medication review (DEU).
- Skin redness/irritation assessment (DEU).
- Documentation of AEs/ADEs (DEU and CGR) and DDs, or follow-up as applicable.
- Finalization of study period.
- Collection of investigational products.
- Pregnancy test (DEU with childbearing potential).
- Questionnaire completion (CGR);
 - o Whether the TENA SmartCare Change Indicator facilitates the decision to change the TENA incontinence product
 - o Likelihood of continued use of the TENA SmartCare Change Indicator.
 - o Perceived wellbeing and comfort of DEU.
 - o Usability

INCLUSION AND EXCLUSION CRITERIA:
Inclusion Criteria

The DEUs and/or CGRs must meet all of the following criteria to be eligible for this clinical investigation:

1. DEU is diagnosed with urinary incontinence managed with a tape-style incontinence product.

2. DEU is unable to sufficiently communicate the need for an incontinence product to be changed.
3. DEU is being cared for in a home environment and most of the care is provided by a main CGR.
4. DEU is willing and able to provide informed consent and to participate in the clinical investigation or has a legally designated representative willing to provide informed consent on behalf of the DEU. Note, the legally designated representative and main CGR cannot be the same person.
5. CGR is willing and able to provide informed consent to participate in the clinical investigation.
6. The CGR frequently checks the saturation level of the incontinence product, manually and/or by a touch-feel process.
7. If incontinence is managed by pharmaceuticals, the dose regime is stable.
8. DEU and CGR ≥ 18 years of age.

Exclusion Criteria

DEUs and/or CGRs meeting any of the following criteria will not be permitted to participate in the clinical investigation:

1. DEU is cared for in a professional establishment or is institutionalized.
2. DEU has ≥ 4 fecal "incidences" per week.
3. DEU has severe incontinence product related skin problems, as judged by the investigator.
4. DEU has any type of urinary catheter(s) resulting in improved/treated urinary incontinence.
5. The incontinence product is changed on a routine based on time (schedule) or device alert, without manual checks.
6. Any other condition that may make participation in the clinical investigation inappropriate, as judged by investigator.
7. CGR is incapable or unwilling to use the required smartphone application and/or the diary registration webpage required for the clinical investigation.
8. Participation in an investigational study of a drug, biologic, or device within 30 days prior to entering the clinical investigation or planned during the course of the clinical investigation.
9. DEU is pregnant or nursing.
10. CGR or DEU with an alcohol or drug addiction

PERFORMANCE AND SAFETY ENDPOINTS:

Primary Endpoint

- Change in the number of manual checks in-between the daily changes of the absorbing incontinence product at week 3 (investigational week) compared to week 1 (baseline week).

Secondary Endpoints

- Incidence of adverse events during week 2 (learning week) and week 3 (investigational week); adverse events (AE), adverse device effects (ADE), serious adverse events (SAE), and serious adverse device effects (SADE), and device deficiency (DD).
- Change in the number of leakages into the clothes and/or bed linen at week 3 (investigational week) compared to week 1 (baseline week).
- Evaluate change in skin redness and irritation, at week 3 (investigational week) compared to week 1 (baseline week).
- Evaluate usability (questionnaire week 2 and 3).
- Evaluate the number of fecal incidences.

STATISTICAL METHODS:

Statistical analysis on variables of interest, including subject demographics, baseline characteristics, performance and safety endpoints will be collected. If nothing else is stated, descriptive statistics will be given for each variable in the investigation. This means number of subjects (n), mean, median, standard deviation (SD), minimum (min) and maximum (max) values will be presented for continuous data and frequencies and percentages for categorical data. The level of significance is set to 5% for all tested variables and specified in section 12.3.

The primary variable is the percentage change of the number of manual checks between week 1 and week 3 of the trial. A one-tailed paired t-test will be used to test if the number of manual checks have been reduced relative to week 1. If the variable is not normally distributed the non-parametric Wilcoxon signed-rank test will be used and in case of a significant result, a one-sided 95% confidence interval will be constructed for the percentage change in checks between week 1 and week 3 to validate at least a 30% reduction.

Performance Analysis

The main analyses will be analyses of changes: investigation week compared to baseline week. Paired comparison will be conducted on the primary and secondary variables. T-test or non-parametric tests will be used (if normality cannot be assumed). The significance level will be set to 5%.

Safety Analysis

Data on incidence and severity of adverse events related to TENA SmartCare Change Indicator will be summarized in terms of AE, ADE, SAE, SADE and DD

All safety variables will be tabulated for the Safety Population.

	Title: POWER Clinical Investigation Plan	Id:
---	--	-----

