During the ongoing marketing of the TENA product line of incontinence products the need for easy-to-use products and solutions to support family caregivers have been identified. Typically, an absorbing incontinence product is changed three to four times per day. Changing too early leads to unutilized products being discarded and changing too late implies a risk of leakages onto garments and furniture as well as risk of moisture-associated skin damage. To provide quality care and reassure that the incontinent individual is comfortable, a family caregiver checks the saturation status of each pad on average 2-3 times between changes, a manual process involving touch-feel, looking, and/or asking that not only implies worry for the caregiver but also is an invasion of the privacy of the incontinent individual being cared for [13].

	Title: POWER Clinical Investigation Plan	Id:
---	---	-----

The aim of this interventional, post-market clinical investigation is to demonstrate the performance and safety of the TENA SmartCare Change Indicator as an accessory to TENA incontinence products. The primary objective is to demonstrate that use of TENA SmartCare Change Indicator has the ability to reduce the number of manual checks by informing the CGR about increasing saturation of the absorbing core. The target population for this clinical investigation is individuals suffering from UI (DEU) who are cared for in a home environment, by one “main” CGR. The clinical investigation will be conducted in compliance with Declaration of Helsinki and the most current version of ISO 14155, and all approvals (i.e. Independent Ethical Committee (IEC) approval and Competent Authority (CA) approval) will be retrieved before study initiation.

The clinical data retrieved from this clinical investigation will be evaluated and incorporated in the product Clinical Evaluation Report (CER).

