8.2 Anticipated adverse device effects

No adverse device effects are anticipated. During the previous clinical investigation (FUEL) no such effects were observed.

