9.2 Secondary Objectives

The secondary objectives are to:

- Evaluate safety through analyzing device-related adverse events reported during the investigation.
- Evaluate leakage into clothes and/or bed linen.
- Evaluate change in skin redness and irritation.
- Evaluate usability.
- Evaluate the number of fecal incidences.

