10 DESIGN OF THE CLINICAL INVESTIGATION

10.1 General

This is a prospective, interventional, post-market clinical investigation with the aim to demonstrate the performance and safety of the TENA SmartCare Change Indicator when used as intended in subjects affected with UI compared to Standard of Care. The outcome will be evaluated and incorporated in the product specific CER and serve as a base for continuous investigations.

Thirty-five (35) DEUs with UI cared for in a home environment mainly by one CGR will be recruited in Poland.

The clinical investigation is designed to be conducted in the individuals home environment, for a duration of three (3) weeks + potential incontinence product training week (one) and potential additional days depending on the visit window scheduling. Eight visits are planned for each subject during the duration of the clinical investigation. However, two of the visits are optional and conducted as needed. If considered necessary by the investigator, nurse, or CGR, additional contacts (e.g. visits/phone calls/video calls) can be arranged. The first week will establish an individual baseline for each EDU, during which the number of manual daily checks between changes of the TENA incontinence product are to be registered by the CGR. During the second week the CGR will be provided the TENA SmartCare Change Indicator and learn how to set up and use it as intended by the manufacturer. During the third week the TENA SmartCare Change Indicator will be used as intended by the manufacturer, while the number of additional manual checks between changes of the TENA incontinence product are to be registered by the CGR. The number of manual checks will be analyzed with regard to the individual baseline in order to evaluate the reduction of manual checks.

The overall duration of the investigation is estimated to 8 months, including a 6-month recruitment period. Expected duration of each subject's participation is 3-6 weeks depending on potential incontinence product training week and potential additional days depending on the visit window scheduling.

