**7.3.2 Analyses**

No statistical analyses are planned for safety parameters. The safety endpoint will be summarized using descriptive statistics.

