**7.3.3 Presentation**

**AE/ADE:**

The following summaries of AEs and SAEs will be given:

- Total number of AEs
- Total number of unique AEs
- Total number of unique, related AEs
- Total number (%) of subjects with at least one AE
- Total number (%) of subjects with at least one related AE
- Total number (%) which had AE as reason for premature discontinuation of study device

Severity, action taken, concomitant therapy started and subject outcome of the AEs will be given in data listings only. AEs, which were reason for premature discontinuation of study device, will be listed separately.

Depending on the number of AEs reported, the most frequently reported (e.g. in more than 5% of the patients) AEs might be summarized separately.

The total number of SAEs and patients with a least one SAE will always be given. Further summaries of SAEs depending on the number of SAEs observed.

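### The stated aim is to *demonstrate* safety but the objective is only to *evaluate* it, and an expected 0% in 24 to 35 DEUs carries an unreported two-sided 95% upper limit of 14.2% to 10.0%

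*Protocol*

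**What the plan says.** **Aim.** The CIP synopsis states: "The purpose of this post market clinical investigation is to demonstrate the performance and safety of the TENA SmartCare Change Indicator". CIP 10.1 describes an investigation "with the aim to demonstrate the performance and safety of the TENA SmartCare Change Indicator when used as intended". CIP 5.1 and SAP 3.2 use the same verb for safety.

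**Objective.** The secondary objective in CIP 9.2, repeated in the synopsis and SAP 3.1.2, is weaker: "Evaluate safety through analyzing device-related adverse events reported during the investigation".

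**Analysis.** SAP 7.3.2: "No statistical analyses are planned for safety parameters. The safety endpoint will be summarized using descriptive statistics". CIP 12.1 likewise limits safety to descriptive and summary statistics. SAP 7.3.3 plans event totals, rows such as "Total number (%) of subjects with at least one related AE", and listings of severity, action taken and outcome. SAE totals and the number of patients with an SAE are always given. SADEs are listed only.

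**Expectation.** CIP 8.2: "No adverse device effects are anticipated". It adds that the previous investigation saw none, without giving its size.

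**Denominator and exposure.** SAP 4.2.1 defines the safety set as all consented subjects. The device is handed over at Visit 3 (CIP 10.5.1.4), and SAP 6.3 estimates exposure at two weeks.

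**The concern.** To demonstrate safety, a trial needs a rate to rule out, or at least a statement of which rates the data exclude. Here the hypothesis (CIP 9.3), sample size (12.2), power (12.3) and pass/fail criterion (12.5) all concern manual checks. The safety part is purely descriptive, which fits the objective but not the aim.

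The gap matters most for the result that the sponsor expects. A bare 0 (0%) says nothing about precision, and it would sit in a report whose stated purpose is to demonstrate safety and whose data go into the Clinical Evaluation Report (CIP 5.1 and 10.1). The denominator may add to the problem: DEUs who consent and leave before Visit 3 count towards the safety percentage without having used the device.

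**Working it through.** **Inputs.** The lower number is from the synopsis: "To demonstrate the primary objective 24 evaluable subjects are needed to complete the investigation". The upper number is 35 recruited, with 30% dropout (CIP 12.2). The documents give no number of exposed DEUs, so I take 24 to 35 as the assumed range and add 20 as an assumed less favourable case.

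**The plan's own figure.** 24 / (1 − 0.30) = 34.3, rounded up to 35. This reproduces the recruitment target. It was set for manual checks; the documents give no precision figure for safety.

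**Zero events among n exposed DEUs.** The exact (Clopper-Pearson) limits are:

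- two-sided 95% upper limit = 1 − 0.025^(1/n)
- one-sided 95% upper limit = 1 − 0.05^(1/n)
- chance of seeing no event at an assumed true two-week rate of 5% = 0.95^n

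| Exposed DEUs | Two-sided 95% upper limit | One-sided 95% upper limit | Chance of zero if true rate is 5% |
|---|---|---|---|
| 35 | 10.0% | 8.2% | 17% |
| 24 | 14.2% | 11.7% | 29% |
| 20 (assumed) | 16.8% | 13.9% | 36% |

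For scale, bringing the zero-event upper limit down to 5% would need 59 exposed DEUs one-sided or 72 two-sided.

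**Effect of the denominator.** As an extreme assumption, let all 35 − 24 = 11 dropouts leave before Visit 3.

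- With no events, the safety set gives an upper limit of 10.0%; the exposed DEUs give 14.2%.
- With one ADE, the safety set gives 1/35 = 2.9% (two-sided 95% interval 0.07% to 14.9%); the exposed DEUs give 1/24 = 4.2% (0.1% to 21.1%).

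The true difference depends on when dropouts occur, which the documents do not predict.

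**The case against.** The other side has a good case, and much of it stands.

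- **The operative text is already modest.** The listed objective is to evaluate safety, the SAP openly calls safety descriptive, and SAP 4.6 names one formal analysis, the primary endpoint. No pass/fail decision rests on safety.
- **The context lowers the stakes.** CIP 7 treats safety as already established, and CIP 6.2.1 gives the device as CE-marked Class I. This supports rewording the aim: what is already established need not be demonstrated again in 35 people.
- **More than percentages is planned.** There are listings, and skin redness and irritation are scored and compared between weeks 1 and 3 (SAP 7.2).
- **The limit can be derived.** It depends only on n when the count is zero, and SAP 5.1 summarises how many subjects attended each visit. A careful reader could work it out.

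A reader might infer that the planned tables hide the uncertainty, or that a zero will be accepted as proof of safety. The documents support neither. Subject numbers are reported, and nothing says that the safety conclusion of the Clinical Evaluation Report rests on this trial alone.

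What remains is that four statements of the aim promise more than the plan delivers, that the interval is left for the reader to compute, and that the safety percentages use a denominator not limited to exposed DEUs.

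**Conclusion.** The point holds as an inexpensive improvement in wording and reporting. The aim and the safety objective use different verbs, and only the objective matches the planned analysis. If no ADE occurs, the data would be compatible, at two-sided 95% confidence, with a per-DEU rate over about two weeks of up to 10.0% (35 exposed) or 14.2% (24 exposed). The limit would be wider if fewer are exposed.

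These figures assume independent DEUs, each counted once, with complete ascertainment over the exposure period. They do not cover caregiver events, for which the plan defines no denominator.

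A reader might go further and conclude that the trial should be powered for safety or should test it formally. The documents do not support that: safety is a secondary, descriptive objective, and the primary analysis is unaffected.

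**What to change.** 1. In the synopsis, CIP 5.1, CIP 10.1 and SAP 3.2, change the aim to *demonstrate the performance and evaluate the safety*.
2. In SAP 7.3.3, report the number and percentage of device-exposed DEUs (those who received the device at Visit 3) with at least one ADE. Add a row for at least one SADE, since no such percentage is now planned.
3. Give each of these an exact (Clopper-Pearson) two-sided 95% confidence interval, including when the count is zero. State in SAP 7.3.2 that the intervals are descriptive.
4. List caregiver events separately, so that they do not enter a percentage based on DEUs.

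**Cost.** One added table row, two intervals and a less favourable safety statement (0% with an upper limit of about 10% to 14%). The CIP wording would go through the amendment process in CIP 14; the SAP changes can be made on their own. No new data, test, multiplicity adjustment or subjects are needed.
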